## Change log

Version No.	Effective Date	Reason for the Change / Revision	Supersedes

## 1 Introduction

### 1.1 General Considerations

This document describes the planned statistical analyses for 000233 DAWN. This SAP is based on the consolidated protocol Ver.5.0, dated 05 July 2018, with changes according to Global Amendments #01, #02, and #03 implemented.

### 1.2 Definitions/ Abbreviations

#### 1.2.1 Definition of Terms

Terms	Definitions
Aggregated Average	Average over post-randomization visits up to and including the current visit
Baseline-ENR	Baseline measurement for the enrichment period, assessed at Visit 2
Baseline-RT	Baseline measurement for the randomized-treatment period, assessed at Visit 4
$\Delta d$	Effect of dose $d$ of FE 201836 compared to placebo
e-Diary	Electronic diary filled out by the participant at home, covering Insomnia Severity Index (ISI), Nocturia Impact Diary (NI diary), Patient Global Impression of Severity (PGI-S), Patient Global Impression of Improvement (PGI-I), HSU 5 point Likert bother scale (Bother), Voiding Diary, and IMP intake
ED85	The minimum dose most likely to have more than 85% of the effect of the maximum dose
Enrichment Period	Period between dispense of single-blind treatment and randomization
FUSP	First Undisturbed Sleep Period (FUSP) is defined as the time in minutes from the time of going to bed to the time of first nocturnal void, or time of awakening if no void occurred
MED	The minimally effective dose defined as the lowest dose that has at least a 0.3 larger reduction in mean nocturnal voids compared to placebo
$\mu d$	The mean dose-response at dose $d$ of FE 201836 corresponding to two nocturnal voids at baseline-RT
Nocturnal diuresis rate	The nocturnal diuresis rate is the ratio of Nocturnal Urine Volume (NUV, mL) to total time in bed (min)
NPi	Nocturnal Polyuria index (NPi) is calculated as the ratio of the nocturnal urine volume (NUV) by the 24-hour urine volume
NUV	Nocturnal Urine Volume (NUV) is the total urine volume from 5 minutes after bedtime with the intention to sleep until the first void within 30 minutes of rising in the morning
Pr(dose <math>d</math> is ED85)	Posterior probability that the dose $d$ is the ED 85
Pr(dose <math>d</math> is MED)	Posterior probability that the dose $d$ is the MED
Pr(<math>\Delta d < -0.3</math>)	Posterior probability that the dose $d$ has at least a 0.3 larger reduction in mean nocturnal voids compared to placebo
Pr(<math>\mu_{500} < \mu_{P1b}</math>)	Posterior probability that 500 $\mu$ g FE 201836 is superior to placebo
Safety-ENR	Safety analysis set for the enrichment period
Safety-RT	Safety analysis set for the randomized-treatment period

## 1.2.2 Abbreviations

Abbreviations	Meaning of abbreviations in document
AE	Adverse Event
ANCOVA	Analysis of Covariance
ATC	Anatomic Therapeutic Chemical
CV	Coefficient of Variation
DMC	Data Monitoring Committee
ECG	Electrocardiogram
ENR	Enrichment Period
FUSP	First Undisturbed Sleep Period
HLGT	High Level Group Term
HLT	High Level Term
IMP	Investigational Medicinal Product
ISI	Insomnia Severity Index
ITT	Intention-To-Treat
MedDRA	Medical Dictionary for Regulatory Activities
MMRM	Mixed Model for Repeated Measurements (repeated-measurements ANCOVA)
NI	Nocturia Impact
NPi	Nocturnal Polyuria index
NUV	Nocturnal Urine Volume
ODT	Orally Disintegrating Tablet
PP	Per-Protocol
PT	Preferred Term
RT	Randomized-treatment Period
SAE	Serious Adverse Event
SOC	System Organ Class
TEAE	Treatment Emergent Adverse Event

### **1.3 Presentation of Results**

#### **1.3.1 Presentation of Descriptive Results**

Categorical data will be summarized, unless otherwise stated, using frequency (n) and relative frequencies as percentage (i.e.  $n/N*100$ ).

Continuous data will be presented for observed values and change from baseline for each visit and at last visit, unless otherwise stated, using the number of subjects (N), mean, standard deviation (SD), median, lower and upper quartiles, minimum, and maximum.

Only table shells for inferential statistics will be provided. End-of-Text and In-Text tables of descriptive statistics follow in-house standards.

#### **1.3.2 Presentation of Inferential Results**

Frequentist inferential results will be presented using the respective point estimates with two-sided 95% confidence intervals unless otherwise stated. Bayesian inferential results are expressed in terms of posterior means and medians and 95% credibility intervals, unless otherwise stated.

Generic table shells per type of analysis will be provided.

#### **1.3.3 Subject Data Listings by Domain**

All subject data will be presented by listings organized in accordance to ICH –E3. More precisely the following listings will be provided:

- Discontinued subjects
- Major protocol deviations
- Subjects (and observations) excluded from the efficacy analysis
- Demographic data
- Compliance
- Individual efficacy response data
- Adverse event listings (each subject)
- Listing of individual laboratory measurements by subject, when required by regulatory authorities

#### **1.3.4 Subject Profiles**

Subject profiles will be created using in-house standard SAS macros.

## 2 Trial Objectives and Endpoints

### 2.1 Objectives

#### Primary Objective

- To establish the dose-response of FE 201836 with respect to the number of nocturnal voids in subjects with nocturia due to NP.

#### Secondary Objectives

- To evaluate responder rates with regards to changes in number of nocturnal voids.
- To psychometrically validate the Nocturia Impact Diary© (NI Diary).
- To evaluate the subject benefit of FE 201836 based on the NI Diary data.
- To evaluate the clinical benefit of FE 201836 based on reduction in nocturnal voiding.
- To evaluate FE 201836 with respect to sleep benefit, i.e., duration of the First Undisturbed Sleep Period (FUSP) and sleep related Patient Reported Outcomes (PROs).
- To evaluate the PD effect of FE 201836 with respect to nocturnal diuresis rate and NP.

#### Safety Objective

- To evaluate the safety profile of FE 201836.

#### Exploratory Objectives

- To explore the biomarker copeptin, an AVP surrogate, to identify low nocturnal vasopressin levels in plasma.
- To explore the dose-response of FE 201836 with respect to total sleep time.
- To explore the association between total sleep time and FUSP.
- To explore the effect of FE 201836 with respect to Nocturnal Polyuria index (NPI).
- To benchmark the efficacy of FE 201836 in relation to desmopressin.

### 2.2 Endpoints

#### Primary Endpoint

- Change from baseline in number of nocturnal voids during 12 weeks of treatment.

#### Secondary Endpoints

- Change from baseline in number of nocturnal voids at Weeks 1, 4, 8 and 12.
- Responder rate defined as 50% reduction in nocturnal voids from baseline at Weeks 1, 4, 8 and 12 during 12 weeks of treatment.
- Change from baseline in NI Diary Total Score at Weeks 1, 4, 8 and 12 and during 12 weeks of treatment.
- Percentage of nights during the treatment period with at most one nocturnal void.

- Percentage of nights during the treatment period with complete response, i.e., with no nocturnal voids.
- Change from baseline in NI Diary Overall Impact Score at Weeks 1, 4, 8 and 12 and during 12 weeks of treatment.
- Patient Global Impression of Improvement (PGI-I) urinary symptoms scores at Weeks 1, 4, 8 and 12.
- Change from baseline in Patient Global Impression of Severity (PGI-S) scores at Weeks 1, 4, 8 and 12.
- Change from baseline in Bother as measured by the Hsu 5-point Likert Bother scale (Hsu, 2015) at Weeks 1, 4, 8 and 12.
- Change from baseline in Insomnia Severity Index (ISI) at Weeks 4, 8 and 12.
- Change from baseline in FUSP at 1, 4, 8 and 12 weeks of treatment and during 12 weeks.
- Change from baseline in nocturnal diuresis rate (hourly) profiles at Week 1 and Week 12.
- Change from baseline in Nocturnal Urine Volume (NUV) at Week 1 and Week 12.

### **Safety Endpoints**

- Incidence and severity of adverse events.
- Incidence of hyponatraemia as measured by serum sodium level throughout the trial.
- Change from baseline in mean 24-hour urine volume at Week 1 and Week 12.
- Clinically significant changes in vital signs and laboratory values.

### **Exploratory Endpoints**

- Responder rates defined as 33%, 60%, 70%, 80%, 90% and 100% reduction from baseline in number of nocturnal voids at Weeks 1, 4, 8 and 12.
- Responder rates defined as 1, 2, and 3 voids reduction from baseline in number of nocturnal voids at Weeks 1, 4, 8 and 12.
- The correlation of copeptin levels to NPi at Visit 2.
- Change from baseline in copeptin levels at Week 12.
- Change from baseline in total sleep time per night at Weeks 1, 4, 8 and 12 and during 12 weeks of treatment.
- Correlation between change from baseline in total sleep time and FUSP at Weeks 1, 4, 8 and 12.
- Change from baseline in NPi at Week 1 and Week 12.

### 3 Trial design

#### 3.1 Design Considerations

##### 3.1.1 General Considerations

DAWN is a randomized, double-blind, placebo-controlled, response-adaptive, dose-finding trial with Desmopressin Orally Disintegrating Tablet (ODT) as a benchmark. The trial has a screening period with a 2-week life-style intervention period and an enrichment phase with a 1-week single-blind treatment with the highest dose of FE 201836 and a 1-week washout period, followed by a randomization to double-blind, double-placebo treatment with placebo, different doses of FE 201836, or desmopressin.

The trial is designed with two stages:

In the first stage of the trial, 125 subjects are randomized in a 2:2:1 allocation ratio to placebo, 500 µg FE 201836, or desmopressin, and an interim analysis for futility is performed.

In the second stage, the subjects are randomized with the allocation ratio 2:7:1 for placebo, active treatment with FE 201836, or desmopressin, respectively. Subjects allocated to FE 201836 are randomized to 50 µg FE 201836, 100 µg FE 201836, 150 µg FE 201836, 250 µg FE 201836, 350 µg FE 201836, or 500 µg FE 201836 according to allocation probabilities determined in the interim analyses according to pre-specified rules. Subsequent interim analyses will be performed every 8 weeks, where futility analyses will be performed and the randomization allocation probabilities to the different FE 201836 doses will be adjusted.

Based on the Bayesian analysis of a baseline-adjusted dose-response curve, the minimum dose most likely to have more than 85% of the effect of the maximum dose ( $ED_{85}$ ), and the dose most likely to be the minimally effective dose (MED, defined as the minimum dose that has more than 0.3 voids reduction in nocturnal voids as compared to placebo) will be identified during the reporting of the trial. There are four posterior probabilities of interest as presented in [Table 1](#):

**Table 1 Posterior Probabilities of Interest**

Quantity of Interest	Posterior Probability within the Trial that:	Objective
$Pr(\mu_{500} < \mu_{Plb})$	the effect of 500 µg FE 201836 during the 12 weeks of randomized treatment is superior to placebo	Proof-of-Concept
$Pr(\Delta_{500} < -0.3)$	500 µg FE 201836 has more than 0.3 voids reduction in nocturnal voids as compared to placebo	Futility
$Pr(\text{dose } d \text{ is MED})$	dose $d$ is the MED	Establish the MED
$Pr(\text{dose } d \text{ is } ED_{85})$	dose $d$ is the $ED_{85}$	Establish $ED_{85}$

In the trial updates of the allocation probabilities, the two posterior probabilities:  $\Pr(\text{dose } d \text{ is MED})$  and  $\Pr(\text{dose } d \text{ is ED}_{85})$ , are used in the updated allocation probability for dose  $d$ . The trial updates are performed as analyses without baseline adjustment, thus, they are not based on the model used for the primary analysis in the reporting of the trial. For additional information, see Section 12.

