The dose-response model will be fitted across all doses, i.e., 0-500 µg, but inference will be made only on the doses that remain open to randomisation e.g., 0-350 µg. That is, the MED and ED₈₅ doses and the inferences with regards to proof-of-concept and futility will be limited to the dose range (i.e., with a maximum dose of 350 µg FE 201836).

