### 3.1.3 Trial Stages

In the first of the two trial stages, an interim Bayesian analysis for futility is performed after 125 subjects have been randomized. The futility stopping rule in the first stage is that a less than 10% posterior probability that 500  $\mu\text{g}$  FE 201836 has  $>0.3$  voids reduction in nocturnal voids as compared to placebo ( $\Pr(\mu_{500} - \mu_{Plb} < -0.3) < 10\%$ ).

The futility stopping rule in the second stage is a less than 5% posterior probability that 500  $\mu\text{g}$  FE 201836 has  $>0.3$  voids reduction in nocturnal voids as compared to placebo ( $\Pr(\mu_{500} - \mu_{Plb} < -0.3) < 5\%$ ).

Bayesian estimates based in the dose-response curve without baseline adjustment will be used to update the allocation probabilities for the different doses of FE 201836 (see Section 12).

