## 14 Deviations From the Trial Protocol

A Full Analysis Set was defined in the protocol. However, none of the analyses specified in the trial protocol were based on the Full Analysis Set, so no Full Analysis Set has been defined in this SAP.

$Pr(\mu_d < \mu_{PLb})$  will be presented only for the 500 µg FE 201836 dose (Proof of Concept) since all doses will have the same probability because of the monotone dose-response curve parameterization; and  $Pr(\mu_d = \mu_{MAX})$  will not be displayed since it always equals 1 for the 500 µg dose, and probabilistically almost surely (that is, with probability 1) equals 0 for all other doses, again because of the monotone dose-response curve parameterization.

For some subjects, the baseline voiding diary is missing due to technical problems in the beginning of the study. The change from baseline in voiding data are considered missing completely at random for these subjects, and the subjects are not included in any analyses involving baseline measurements of voiding data.

Two sensitivity analyses have been added:

- Estimates of all quantities of interest based on the Bayesian analysis of the longitudinal model will be presented.
- A Bayesian analysis of the primary outcome with imputation using the level corresponding to placebo for drop-out.

The first sensitivity analysis presents the result for the model used for imputation. The second analysis is the Bayesian equivalent to the frequentist approach specified in the trial protocol based on a mixed model for repeated measurement (repeated-measurements ANCOVA) using MNAR placebo-based pattern mixture model.

Linear trend estimates have been added to the above mentioned protocol-specified frequentist approach as supplements to the description of the association with dose in case there are difficulties with the convergence for the primary analysis or very large uncertainties on the estimated  $\alpha$  parameters.

A secondary analysis of aggregated average change from baseline in nocturnal urine volume has been added. This outcome variable was added to comply with the Bayesian analysis mentioned in Table 9-4 in the trial protocol.

The ITT-RT data set will be used for all secondary analyses as stated in the protocol; but only observed data will be used. This is considered a clarification of the protocol.

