In addition to the illustrations of the therapeutic window specified in the protocol, illustrations of the therapeutic window will be produced using the estimated treatment contrast compared to placebo for the change from baseline-RT to lowest post-baseline measurement of serum sodium as the safety indicator. The inclusion of desmopressin in the plots illustrating the therapeutic window (“Corresponding efficacy and safety of desmopressin will be illustrated in a side panel for comparison.”) has been deleted to comply with “None of the primary, secondary or explorative analyses will include desmopressin.” (Section 10.1).

In the analyses of time to ‘confirmed’ hyponatraemia episodes, the time to event is defined as the time of confirmation in stead of the time to first measurement below the threshold to avoid conditioning on the future. The protocol states “The associated relative hazards of treatment and gender will be analysed using Cox proportional hazards model adjusting for baseline serum sodium and age (<65,  $\geq$ 65 years). Possible heterogeneity between the genders in the relative treatment hazards will be explored by the inclusion of a treatment-by-gender interaction term”. These analyses will not be performed since the trial is too small to perform Cox regression analyses of the occurrence of hyponatraemia events with 9 treatment groups and 2 covariates.

The adverse events tables presenting incidences of least 5% have been changed to presenting at incidences of at least 10% because it is expected that for several of the FE 201836 treatment groups, 20 subjects or less are allocated to the group.

According to [REDACTED], the interim analyses will deviate from the Appendix 2 in the protocol regarding the derivation of the allocation probabilities by the factor  $1/(n_d + 1)$  before the normalization to sum to 1.

Remaining changes are all considered clarifications of presentations specified in the protocol.

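### If the DMC lowers the maximum dose to 350 µg, the SAP still judges futility on 500 µg and can name it as MED or ED85, contrary to protocol 9.11.1

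*SAP*

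**What the plan says.** **Protocol.** Section 9.11.1 (and the Synopsis, under the heading on lowering the maximum dose) provides for a reduction from 500 to 350 µg on DMC recommendation. The model then still uses all doses from 0 to 500 µg, "but inference will be made only on the doses that remain open to randomisation e.g"., 0-350 µg. The text applies this to MED, ED85, proof-of-concept and futility. Tables 9-2 and 9-3 write the criteria with µ_MAX.

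**SAP.**
- Table 1 defines the futility quantity as the probability that "500 µg FE 201836 has more than 0.3 voids reduction in nocturnal voids as compared to placebo". Sections 3.1.3 and 12 use the same dose at the first interim (threshold 10%) and at all later ones (5%).
- Table 1 defines proof-of-concept as the probability that "the effect of 500 µg FE 201836 during the 12 weeks of randomized treatment is superior to placebo".
- Section 10.2.1 derives Pr(dose d is MED) and Pr(dose d is ED85) over a dose list that includes 500 µg.
- Section 1.2.1 defines ED85 as "The minimum dose most likely to have more than 85% of the effect of the maximum dose", without naming that dose. Section 14 equates the maximum with 500 µg: the probability that a dose attains the maximum "will not be displayed since it always equals 1 for the 500 µg dose".
- No section covers a lowered maximum. Section 14 lists deviations without mentioning one, and closes with "Remaining changes are all considered clarifications of presentations specified in the protocol".

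**The concern.** The SAP is not silent on futility. It states a rule on a named dose, so a programmer who follows it after a reduction departs from protocol 9.11.1 without any signal that this has happened. The branch exists for a hyponatraemia signal in the run-in. In that case the trial's remaining questions are whether any open dose works and which open dose is the MED or ED85. A futility look at 500 µg can keep the trial going on an effect that no open dose has, and the dose-finding summary can report a dose that is closed.

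**Working it through.** **Inputs.** Scenario parameters (maximum effect α2, ED50 α3, slope α4) from protocol Appendix 2, Section 4.1.1; placebo effect 0; SD 0.95; MED margin 0.3 voids; ED85 fraction 0.85; doses 50, 100, 150, 250, 350 and 500 µg.

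**Formulas.** f(d) = d^α4 / (d^α4 + α3^α4) and effect(d) = α2·f(d). ED85 solves f(d) = 0.85·f(M), where M is the reference maximum. MED solves |α2|·f(d) = 0.3.

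**Reproducing Appendix 2.** With M = 500 µg, ED85 is 228, 297, 297, 417 and 368 µg for Scenarios I-V, an exact match. Using the asymptote gives 231, 309, 309, 435 and 373, which does not match. MED is 263, 221, 368 and 300 µg for II-V, also exact. So the design simulations took the 500 µg effect as the ED85 reference.

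**Changing the reference to 350 µg.** Grid values are the lowest trial dose that qualifies.

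| Scenario | Effect at 350 | Effect at 500 | Ratio 350/500 | Grid ED85, M = 500 | Grid ED85, M = 350 | Grid MED, all doses | Grid MED, open doses |
|---|---|---|---|---|---|---|---|
| I | -0.290 | -0.298 | 0.975 | 250 | 250 | none | none |
| II | -0.361 | -0.390 | 0.927 | 350 | 350 | 350 | 350 |
| III | -0.452 | -0.488 | 0.927 | 350 | 350 | 250 | 250 |
| IV | -0.250 | -0.473 | 0.529 | 500 | 350 | 500 | none |
| V | -0.465 | -0.590 | 0.787 | 500 | 350 | 350 | 350 |

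Example, Scenario IV at 350 µg: d equals the ED50, so f = 0.5 and the effect is -0.5 × 0.5 = -0.250, short of 0.3. With M = 350 µg the exact ED85 values are 220, 270, 270, 337 and 326 µg.

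**Direction of the futility rule.** On any posterior draw with α2 < α1, Δ_500 is at least as large a reduction as Δ_350. On any other draw neither reaches -0.3. Hence Pr(Δ_500 < -0.3) ≥ Pr(Δ_350 < -0.3) always, and the SAP rule stops less readily.

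**Size (illustration).** Sigmoid fitted with the documented α priors, σ fixed at 0.95, no baseline term, observed arm means set to the scenario truth, and an assumed 50 subjects on placebo, 25 on 350 µg and 25 on 500 µg.

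| Scenario | Pr(Δ_500 < -0.3) | Pr(Δ_350 < -0.3) |
|---|---|---|
| I | 0.49 | 0.33 |
| II | 0.65 | 0.47 |
| III | 0.81 | 0.67 |
| IV | 0.69 | 0.44 |
| V | 0.89 | 0.75 |

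In the Scenario IV fit, 500 µg is the most likely ED85 (0.56) and the most likely MED (0.26). With the cap, 350 µg is the most likely ED85 (0.68). The proof-of-concept probability is 0.973 at both doses.

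**Early closure (illustration).** Protocol 4.2.2.1 allows closure before the first interim, and Table 9-7 shows the DMC trigger can be met with 10 run-in completers, so 500 µg might have few or no randomised subjects. Take 50 on placebo, 50 on 350 µg, none on 500 µg and no true effect. With both arm means at -1 void (the centre of the placebo prior), Pr(Δ_500 < -0.3) is 0.16 and Pr(Δ_350 < -0.3) is 0.03; with both at 0 they are 0.21 and 0.04. Against the 10% threshold the SAP quantity continues and the capped one stops. The 500 µg figure here is extrapolation from the prior.

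**The case against.** The strongest reply is that the SAP is based on protocol version 5.0 and revokes nothing in 9.11.1, that interim conduct is also governed by a DMC charter that is not public, and that the whole matter depends on a DMC decision that may never come. In the base case the two documents agree. All of that stands, and it limits the weight of the point. It does not remove the conflict, because the SAP gives an explicit futility rule with no exception.

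Five stronger readings are tempting, and the documents do not support them.
- *The proof-of-concept verdict could change.* It cannot. Section 14 reports that probability only at 500 µg "since all doses will have the same probability because of the monotone dose-response curve parameterization", and the sigmoid bears this out. For proof-of-concept the mismatch is one of labelling.
- *The SAP fixes the ED85 reference at 500 µg.* Its definition says only the maximum dose. The 500 µg reading comes from Section 14 and from the protocol's own base-case definition. After a reduction the term is ambiguous.
- *The protocol chose µ_MAX to serve the dose-reduction branch.* Nothing says so. Section 9.11.2 words the first-interim rule for 500 µg, and Table 9-2 defines µ_MAX through the dose most likely to have the largest effect.
- *Subjects would still be allocated to 500 µg.* Protocol 4.2.2.1 and the Synopsis close that arm. What is left open is that SAP Section 12 does not say the weights are renormalised over open doses.
- *The futility decision would be reversed in Scenario IV.* At the expected data, 0.69 and 0.44 both lie far above 5% and 10%, so neither rule stops. A rough single-look check with sampling noise over three assumed allocations, at the 5% threshold, gave Scenario IV stopping of about 0.5-2% on 500 µg and 5-8% on 350 µg. With no true effect the gap was wider: about 33-66% against 61-84%.

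**Conclusion.** The point holds as a conditional omission. If the DMC closes 500 µg, the SAP as written judges futility on a dose that protocol 9.11.1 takes out of the inference. It also leaves that dose eligible as MED or ED85, and Section 14 does not declare either. Section 14 does disclose that 500 µg is treated as the maximum because the curve is monotone; what is missing is the lowered-maximum branch.

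The dose-naming effect is exact at the scenario truths: ED85 changes in IV and V, MED in IV only, and nothing changes in I-III. The futility effect is a lower readiness to stop, largest when no dose works or when 500 µg has few subjects. Its direction follows from the monotone curve. Its size rests on the assumed allocations, fixed σ and absence of a baseline covariate, so the posterior and stopping figures are not operating characteristics. Proof-of-concept is unaffected. Given the low cost, the SAP should be corrected.

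**What to change.** Reconcile the SAP with protocol 9.11.1:
- Define d_max as the highest FE 201836 dose open to randomisation at the analysis in question.
- In Table 1 and Sections 3.1.3 and 12, state futility on Δ_dmax. In Table 1 and Section 10.2.1, state proof-of-concept on µ_dmax, for consistent labelling only.
- Define ED85 relative to d_max.
- Compute Pr(dose d is MED), Pr(dose d is ED85) and the normalised allocation weights over open doses only.
- Keep any 500 µg data in the curve fit, as the protocol requires, and cross-refer to 9.11.1.

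The cost is SAP wording and one index in the interim and final programs. Nothing changes while 500 µg stays open. The change should be in place before any unblinded analysis that follows a closure.
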